- **Hepatotoxicity:** Hepatotoxicity as evidenced in the adjuvant study, by increase in transaminases (57% vs. 34%) and alkaline phosphatase (42% vs. 20%) was observed more commonly in the oxaliplatin combination arm than in the control arm. The incidence of increased bilirubin was similar on both arms. Changes noted on liver biopsies include: peliosis, nodular regenerative hyperplasia or sinusoidal alterations, perisinusoidal fibrosis, and veno-occlusive lesions. Hepatic vascular disorders should be considered, and if appropriate, should be investigated in case of abnormal liver function test results or portal hypertension, which cannot be explained by liver metastases.
- **Cardiovascular Toxicity:** QT prolongation and ventricular arrhythmias including fatal Torsade de Pointes have been reported in postmarketing experiences following oxaliplatin administration. ECG monitoring is recommended if therapy is initiated in patients with congestive heart failure, bradycardias, drugs known to prolong the QT interval, including Class Ia and III antiarrhythmics, and electrolyte abnormalities. Correct hypokalemia or hypomagnesemia prior to initiating oxaliplatin and monitor these electrolytes periodically during therapy. Avoid oxaliplatin in patients with congenital long QT syndrome.
- **Rhabdomyolysis:** Rhabdomyolysis, including fatal cases, has been reported in patients treated with oxaliplatin. Discontinue oxaliplatin if any signs or symptoms of rhabdomyolysis occur.

Refer to current package insert for full prescription drug information for oxaliplatin.

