3.2.1 Dose Limiting Toxicity

Using the NCI-CTCAE version 4.0, the following adverse events will be considered dose limiting toxicity (DLT) if occurring during the first cycle (21 days) of treatment and deemed to be related to study treatment:

- Grade 4 neutropenia, thrombocytopenia or anemia.
- Grade ≥ 3 neutropenia or thrombocytopenia lasting over 7 days.
- Grade 3 thrombocytopenia associated with bleeding.
- Neutropenic fever.
- Grade ≥ 3 nausea/vomiting or diarrhea lasting ≥ 3 days despite adequate supportive measures.
- Grade ≥ 3 ALT, AST, or bilirubin elevation > 7 days.
- Grade ≥ 3 non-hematologic toxicity excluding alopecia, anorexia, fatigue, hypertension, isolated lab abnormalities (not clinically significant) and/or allergic or idiosyncratic reactions to any of the study drugs. Anorexia, fatigue and hypertension will be considered as DLT only if they reach Grade 4 or are considered unmanageable.
- Treatment delay of ≥ 14 days for Cycle 2 due to unresolved treatment-related toxicity.

Management and dose modifications associated with all adverse events are outlined in Section 7.0.

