 - Grade 3 uveitis, pneumonitis, bronchospasm, diarrhea, colitis, neurologic toxicity, hypersensitivity reaction, or infusion reaction of *any duration* requires discontinuation
 - Grade 3 laboratory abnormalities do not require treatment discontinuation except Grade 3 thrombocytopenia > 7 days OR associated with bleeding requires discontinuation
 - Any liver function test (LFT) abnormality that meets the following criteria:

- AST or ALT > 8 x ULN
- Total bilirubin > 5 x ULN
- Concurrent AST or ALT > 3 x ULN and total bilirubin > 2 x ULN
- Any Grade 4 adverse event or laboratory abnormality, except for the following events:
 - Grade 4 amylase or lipase abnormalities that are not associated with symptoms or clinical manifestations, or radiographic signs of pancreatitis
 - Isolated Grade 4 electrolyte imbalances/abnormalities that are not associated with clinical sequelae and are corrected with supplementation/appropriate management within 3 days of their onset
 - Grade 4 endocrinopathy adverse events such as adrenal insufficiency, ACTH deficiency, hyper- or hypothyroidosis, or glucose intolerance, which resolve or are adequately controlled with physiologic hormone replacement (steroids, thyroid hormones) or glucose controlling agents, respectively, retreatment can be considered
- Any dosing interruption lasting > 6 weeks with the following exceptions:
 - Dosing interruptions to allow for prolonged steroid tapers to manage treatment-related adverse events are allowed
 - Dosing interruptions > 6 weeks that occur for non-treatment-related reasons may be allowed
- Any adverse event, laboratory abnormality, or intercurrent illness which, in the judgment of the Investigator, presents a substantial clinical risk to the subject with continued pembrolizumab or lanreotide depot dosing

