7.1 Dose Modifications

Subjects experiencing one or more AEs due to the study drug(s) may require dose modification(s) as described in [Section 7.1.1](#) and [Section 7.1.2](#). At the discretion of the Investigator, dose modifications are permitted outside of the those provided in the protocol if the Investigator feels it is in the interest of the subject's safety (e.g., due to multiple toxicities, persistent toxicities, intercurrent illness, or short term compliance or monitoring issues, etc.).

Subjects may need to be followed at least weekly when any study drug is held for toxicity until the toxicity returns to Grade ≤ 1 or is determined to be chronic or irreversible.

Dosing interruptions are permitted in the case of medical / surgical events or logistical reasons not related to study therapy (e.g., elective surgery, unrelated medical events, patient vacation, and/or holidays). Subjects should be placed back on study therapy within 4 weeks of the scheduled interruption, unless otherwise discussed with the Lead PI. The reason for interruption should be documented in the patient's study record. Dosing may be interrupted if there is a need for local palliative radiation therapy, with the approval of the lead PI. In this case, protocol-based therapy cannot be resumed until patients are at least 14 days out from the end of radiation.

If pembrolizumab is permanently discontinued, the subject will be discontinued from study treatment. Maximum duration of treatment for pembrolizumab will be up to 35 cycles. If patients discontinue oxaliplatin due to intolerance, they can be maintained on capecitabine and pembrolizumab. If capecitabine is not tolerated, pembrolizumab monotherapy may be continued. Re-introduction of oxaliplatin is permitted provided neuropathy has improved.

All dose modifications and reasons for modification must be recorded in the CRF.

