OTHER CLINICALLY SIGNIFICANT* NON-HEMATOLOGIC ADVERSE EVENTS			
ToxicityGrade^a	Occurrence	Oxaliplatin	Capecitabine
Grade 1	Any	Maintain dose	Maintain dose
Grade 2	1 st	Hold until grade ≤ 1 , then resume at 80% of current dose ^c	Hold until grade ≤ 1 , then resume at 80% of current dose

OTHER CLINICALLY SIGNIFICANT* NON-HEMATOLOGIC ADVERSE EVENTS			
ToxicityGrade^a	Occurrence	Oxaliplatin	Capecitabine
	2 nd and higher	Hold until grade ≤ 1, then resume at current dose. ^{b,c}	Hold until grade ≤ 1, then resume at 80% of current dose
Grade 3	1 st	Hold until grade ≤ 1, then resume at 80% of current dose ^c	Hold until grade ≤ 1, then resume at 80% of current dose
	2 nd and higher	Hold until grade ≤ 1, then resume at current dose. ^{b,c}	Hold until grade ≤ 1, then resume at 80% of current dose
Grade 4	1 st	Hold until grade ≤ 1, then resume at 60% of current dose ^c	Hold until grade ≤ 1, then resume at 60% of current dose
	2 nd and higher	Hold until grade ≤ 1, obtain permission of PI to resume at 60% of current dose ^b	Hold until grade ≤ 1, obtain permission of PI to resume at 60% of current dose ^b

a. National Cancer Institute Common Terminology Criteria Version 3.0

b. Continued treatment if it is considered to be in the best interest of the patient.

c. **NOTE:** After Cycle 1, at the discretion of the treating physician, once there is recovery of the toxicity to grade ≤ 1, the treating physician may choose, instead of lowering the dose of capecitabine, to hold oxaliplatin and continue capecitabine and pembrolizumab at current dose as clinically indicated. If toxicity recurs, follow original dose modification instructions for capecitabine. If the treating physician chooses to restart oxaliplatin later in the patient's treatment course, the dose of oxaliplatin at which the patient restarts should be one dose level lower than last dose level on which patient was treated. The specific treatment approach used and dose modifications that occur are required to be reported in the Case Report Forms.

* Dose adjustments only for clinically significant toxicities (e.g. asymptomatic lab abnormalities do not necessarily require dose modifications) If non-hematologic toxicities can be attributed solely to either oxaliplatin, capecitabine, or pembrolizumab then no dose adjustments of the other agents are needed.

HEMATOLOGIC ADVERSE EVENTS			
ToxicityGrade ^a	Occurrence	Oxaliplatin	Capecitabine
NEUTROGENIA			
Grade 1	Any	Maintain dose	Maintain dose

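### The Section 1.2.2 instruction to discontinue oxaliplatin for rhabdomyolysis is missing from Section 7, whose default is to maintain the dose or to hold and resume

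*Combined protocol and SAP*

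**What the plan says.** Section 1.2.2 lists serious reactions to oxaliplatin taken from the package insert. The rhabdomyolysis entry notes that fatal cases have been reported and instructs: "Discontinue oxaliplatin if any signs or symptoms of rhabdomyolysis occur". It sets no grade threshold and no attribution condition.

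Section 3.2.1 states: "Management and dose modifications associated with all adverse events are outlined in Section 7.0". Section 7 contains no rule for rhabdomyolysis or any other muscle toxicity of oxaliplatin. Its special guidelines for that drug (numbered 7.2.1.2) cover neurotoxicity, laryngopharyngeal dysesthesia, hypersensitivity and pulmonary fibrosis.

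Section 7.1.2 has a residual table for other non-hematologic events. For oxaliplatin it keeps the dose at Grade 1. For a first Grade 2 or first Grade 3 event it says "Hold until grade ≤ 1 , then resume at 80% of current dose". Two footnote provisions limit it: "Dose adjustments only for clinically significant toxicities", and "If non-hematologic toxicities can be attributed solely to either oxaliplatin, capecitabine, or pembrolizumab then no dose adjustments of the other agents are needed".

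**The concern.** The protocol gives two different actions for the same event. The stop instruction sits in the Introduction, while the section that sites are told to use for managing toxicity leads to continued dosing or a default restart. Fatal cases have been reported, so the operative section should carry the stop rule. At stake is the safety of an occasional patient. No efficacy estimate or error rate is involved.

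**Working it through.** The protocol states no figure to reproduce on this point. The check sets the texts side by side.

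**1. Is there a rhabdomyolysis rule elsewhere in Section 7?** No. Sections 7.1.1, 7.1.2, the capecitabine and oxaliplatin special guidelines, and Section 7.2 do not name it. The residual table therefore applies by default.

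**2. What does that table do?** The starting dose is 130 mg/m² (Table 3.1 and Section 6.3.2).

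| Event attributed to oxaliplatin | Residual table, Section 7.1.2 | Dose (mg/m²) | Section 1.2.2 |
|---|---|---|---|
| Grade 1 | Maintain | 130 | Discontinue |
| First Grade 2 or 3 | Hold, resume at 80% | 0.80 × 130 = 104 | Discontinue |
| Second or later Grade 2 or 3 | Hold, resume at current dose if in the patient's best interest | 104 | Discontinue |
| First Grade 4 | Hold, resume at 60% | 0.60 × 130 = 78 | Discontinue |
| Second or later Grade 4 | Hold; PI permission needed to resume at 60% of current dose | n/a | Discontinue |

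No row discontinues oxaliplatin. At Grade 1 the conflict is direct. At Grades 2 to 4 both texts stop the drug at onset, and they differ on the default restart.

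**3. Do the pembrolizumab rules close the gap?** Only in part. Rhabdomyolysis is an expected pembrolizumab reaction (Table 1.2.1.3.1). Among events attributed to pembrolizumab, Section 5.7 requires stopping for "Any Grade 4 adverse event or laboratory abnormality, except for the following events", and Section 7.1 adds: "If pembrolizumab is permanently discontinued, the subject will be discontinued from study treatment". A Grade 4 case attributed wholly or partly to pembrolizumab therefore ends all study treatment. So does a pembrolizumab-attributed Grade 3 event that recurs (Section 7.1.1) or lasts more than 7 days (Section 5.7). The 78 mg/m² restart arises only when pembrolizumab is excluded as a cause. None of these rules covers a case attributed to oxaliplatin alone.

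**4. What does discontinue mean in Section 1.2.2?** The same list bars rechallenge outright for hypersensitivity, and for pulmonary toxicity it stops the drug only until lung disease is excluded. The rhabdomyolysis entry carries neither wording. With no condition for resuming, permanent stopping is the natural reading, but it is not written.

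**5. Were comparable warnings carried over?** Yes. The oxaliplatin special guidelines stop the drug for Grade 3 or 4 hypersensitivity and for confirmed pulmonary fibrosis. The rhabdomyolysis warning was not carried over.

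**6. How often might this arise?** The documents give no oxaliplatin rate. As an assumption for scale only, take the pembrolizumab count: 1 case (Table 1.2.1.3.1) in 2,799 subjects (Table 1.2.1.3.2, same reference dataset).

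- Rate: 1 / 2,799 = 0.000357, or 0.036%. Exact (Clopper-Pearson) 95% CI: 0.0000090 to 0.00199.
- Expected cases in 35 patients: 35 × 0.000357 = 0.0125. Range: 35 × 0.0000090 = 0.0003 to 35 × 0.00199 = 0.070.

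**The case against.** The strongest reply is that the two texts are not rival rules. The Section 1.2.2 entry is a package-insert summary, a specific warning can be read as prevailing over a generic table, and Section 3.2.1 does not call Section 7 exhaustive. A careful site could follow both. That is possible, but it depends on the site looking in the Introduction for a dosing instruction, and nothing in Section 7 sends it there.

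Second, permanence is unwritten. If discontinue allows a restart after recovery, the conflict at Grades 2 to 4 disappears. This stands as a limit on the restart part of the point. The Grade 1 conflict does not depend on it, although the documents do not say how rhabdomyolysis is graded or whether a Grade 1 category exists.

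Third, safeguards exist. Section 7.1 says "dose modifications are permitted outside of the those provided in the protocol" where subject safety calls for it. A footnote to the table lets the physician keep oxaliplatin on hold, Section 5.7 allows discontinuation when continuing is unsafe, and a case meeting SAE criteria reaches the Lead PI (Section 10.2). These make inadvertent re-dosing unlikely. They permit the drug to stay off without telling the site to keep it off.

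Fourth, the note in Section 7.1.1 on life-threatening and recurrent Grade 3 toxicity is worded without naming a drug. Read literally, it could rule out those restarts whatever the cause. It sits under the pembrolizumab heading and refers to the pembrolizumab table, so it is not a clear oxaliplatin rule.

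Finally, the frequency figure is borrowed from another drug. That is correct, and it is used for scale only.

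**Conclusion.** The concern holds, as a minor patient-safety inconsistency. Section 7 omits a stop instruction given elsewhere in the protocol and leaves an oxaliplatin-attributed case to a table that maintains or resumes dosing: 130 mg/m² at Grade 1, 104 mg/m² after a first or second Grade 2 or 3 event, and 78 mg/m² after a first Grade 4 event with pembrolizumab excluded. Section 1.2.2 implies 0 if discontinue is permanent. This assumes that the event is judged clinically significant and that the site follows the default. If a mild case is judged not significant, the footnote calls for no adjustment and dosing still continues. Far fewer than one case would be expected in 35 patients on the borrowed rate. PFS, power and sample size are unaffected.

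**What to change.** Add to the oxaliplatin special guidelines in Section 7, next to the pulmonary fibrosis rule:

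> *Stop oxaliplatin at any sign or symptom of rhabdomyolysis, whatever the grade. Do not restart unless the investigator's work-up excludes rhabdomyolysis; if it is confirmed or cannot be excluded, discontinue oxaliplatin permanently. This rule overrides the residual non-hematologic table in Section 7.1.2 and its sole-attribution footnote.*

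This follows the existing pulmonary rule of stopping, investigating and terminating on confirmation. It also states what happens when the work-up is inconclusive.

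The cost is three sentences at the next amendment, with no added patients or scheduled visits. A suspected case may need a creatine kinase test, which is not in Appendix E and would be ordered only when clinically indicated. The downside is that an occasional patient will stop oxaliplatin for an event caused by another drug. Under Section 7.1 such a patient could stay on capecitabine and pembrolizumab, provided pembrolizumab has not been permanently discontinued.

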1.2.3 Capecitabine

Capecitabine (Xeloda®) is a nucleoside metabolic inhibitor with antineoplastic activity. It is FDA-approved for the following indications: 1) adjuvant colon cancer (patients with Dukes' C colon cancer); 2) metastatic colorectal cancer (first-line as monotherapy when treatment with fluoropyrimidine therapy alone is preferred); and 3) metastatic breast cancer (in combination with docetaxel after failure of prior anthracycline-containing therapy or as monotherapy in patients resistant to both paclitaxel and an anthracycline-containing regimen).

Mechanism of Action

Enzymes convert capecitabine to 5-fluorouracil (5-FU) in vivo. Both normal and tumor cells metabolize 5-FU to 5-fluoro-2'-deoxyuridine monophosphate (FdUMP) and 5-fluorouridine triphosphate (FUTP). These metabolites cause cell injury by two different mechanisms. First, FdUMP and the folate cofactor, N5,10-methylenetetrahydrofolate, bind to thymidylate synthase (TS) to form a covalently bound ternary complex. This binding inhibits the formation of thymidylate from 2'-deoxyuridylate. Thymidylate is the necessary precursor of thymidine triphosphate, which is essential for the synthesis of DNA, so that a deficiency of this compound can inhibit cell division. Second, nuclear transcriptional enzymes can mistakenly incorporate FUTP in place of uridine triphosphate (UTP) during the synthesis of RNA. This metabolic error can interfere with RNA processing and protein synthesis.

Adverse Events

Most common adverse reactions ($\geq 30\%$) were diarrhea, hand-and-foot syndrome, nausea, vomiting, abdominal pain, fatigue/weakness, and hyperbilirubinemia.

The following are Warnings and Precautions as discussed in package insert dated December 2016¹⁵:

- **Coagulopathy:** Patients receiving concomitant capecitabine and oral coumarin-derivative anticoagulant therapy should have their anticoagulant response (INR or prothrombin time) monitored closely with great frequency and the anticoagulant dose should be adjusted accordingly.
- **Diarrhea:** Capecitabine can induce diarrhea, sometimes severe. Patients with severe diarrhea should be carefully either metastatic breast or colorectal cancer who received capecitabine monotherapy, the median time to first occurrence of grade 2 to 4 diarrhea was 34 days (range from 1 to 369 days). The median duration of grade 3 to 4 diarrhea was 5 days. National Cancer Institute of Canada (NCIC) grade 2 diarrhea is defined as an increase of 4 to 6 stools/day or nocturnal stools, grade 3 diarrhea as an increase of 7 to 9 stools/day or incontinence and malabsorption, and grade 4 diarrhea as an increase of ≥ 10 stools/day or grossly bloody diarrhea or the need for parenteral support.

Necrotizing enterocolitis (typhlitis) has been reported.

- **Cardiotoxicity:** The cardiotoxicity observed with capecitabine includes myocardial infarction/ ischemia, angina, dysrhythmias, cardiac arrest, cardiac failure, sudden death, electrocardiographic changes, and cardiomyopathy. These adverse reactions may be more common in patients with a prior history of coronary artery disease.
- **Dihydropyrimidine Dehydrogenase Deficiency (DPD):** Based on postmarketing reports, patients with certain homozygous or certain compound heterozygous mutations in the DPD gene that result in complete or near complete absence of DPD activity are at increased risk for acute early-onset of toxicity and severe, life-threatening, or fatal adverse reactions caused by capecitabine (e.g., mucositis, diarrhea, neutropenia, and neurotoxicity). Patients with partial DPD activity may also have increased risk of severe, life-threatening, or fatal adverse reactions caused by capecitabine.

- **Dehydration and Renal Failure:** Dehydration has been observed and may cause acute renal failure which can be fatal. Patients with pre-existing compromised renal function or who are receiving concomitant capecitabine with known nephrotoxic agents are at higher risk. Patients with anorexia, asthenia, nausea, vomiting or diarrhea may rapidly become dehydrated.
- **Embryo-Fetal Toxicity:** Based on findings from animal reproduction studies and its mechanism of action, capecitabine may cause fetal harm when given to a pregnant woman. Limited available data are not sufficient to inform use of capecitabine in pregnant women. In animal reproduction studies, administration of capecitabine to pregnant animals during the period of organogenesis caused embryoletality and teratogenicity in mice and embryoletality in monkeys at 0.2 and 0.6 times the exposure (AUC) in patients receiving the recommended dose respectively. Apprise pregnant women of the potential risk to a fetus. Advise females of reproductive potential to use effective contraception during treatment and for 6 months following the last dose of capecitabine.
- **Mucocutaneous and Dermatologic Toxicity:** Severe mucocutaneous reactions, some with fatal outcome, such as Stevens-Johnson syndrome and Toxic Epidermal Necrolysis (TEN) can occur in patients treated with capecitabine. Hand-and-foot syndrome (palmar-plantar erythrodysesthesia or chemotherapy-induced acral erythema) is a cutaneous toxicity. Median time to onset was 79 days (range from 11 to 360 days) with a severity range of grades 1 to 3 for patients receiving capecitabine monotherapy in the metastatic setting.
- **Hyperbilirubinemia:** In 875 patients with either metastatic breast or colorectal cancer who received at least one dose of capecitabine 1250 mg/m² twice daily as monotherapy for 2 weeks followed by a 1-week rest period, grade 3 (1.5-3 x ULN) hyperbilirubinemia occurred in 15.2% (n=133) of patients and grade 4 (>3 x ULN) hyperbilirubinemia occurred in 3.9% (n=34) of patients. Of 566 patients who had hepatic metastases at baseline and 309 patients without hepatic metastases at baseline, grade 3 or 4 hyperbilirubinemia occurred in 22.8% and 12.3%, respectively. Of the 167 patients with grade 3 or 4 hyperbilirubinemia, 18.6% (n=31) also had postbaseline elevations (grades 1 to 4, without elevations at baseline) in alkaline phosphatase and 27.5% (n=46) had postbaseline elevations in transaminases at any time (not necessarily concurrent). The majority of these patients, 64.5% (n=20) and 71.7% (n=33), had liver metastases at baseline. In addition, 57.5% (n=96) and 35.3% (n=59) of the 167 patients had elevations (grades 1 to 4) at both prebaseline and postbaseline in alkaline phosphatase or transaminases, respectively. Only 7.8% (n=13) and 3.0% (n=5) had grade 3 or 4 elevations in alkaline phosphatase or transaminases.

In the 596 patients treated with capecitabine as first-line therapy for metastatic colorectal cancer, the incidence of grade 3 or 4 hyperbilirubinemia was similar to the overall clinical trial safety database of capecitabine monotherapy. The median time to onset for grade 3 or 4 hyperbilirubinemia in the colorectal cancer population was 64 days and median total bilirubin increased from 8 µm/L at baseline to 13 µm/L during treatment with capecitabine. Of the 136 colorectal cancer patients with grade 3 or 4 hyperbilirubinemia, 49 patients had grade 3 or 4 hyperbilirubinemia as their last measured value, of which 46 had liver metastases at baseline.

In 251 patients with metastatic breast cancer who received a combination of capecitabine and docetaxel, grade 3 (1.5 to 3 x ULN) hyperbilirubinemia occurred in 7% (n=17) and grade 4 (>3 x ULN) hyperbilirubinemia occurred in 2% (n=5).

- **Hematologic:** In 875 patients with either metastatic breast or colorectal cancer who received a dose of 1250 mg/m² administered twice daily as monotherapy for 2 weeks followed by a 1-week rest period, 3.2%, 1.7%, and 2.4% of patients had grade 3 or 4 neutropenia, thrombocytopenia or

decreases in hemoglobin, respectively. In 251 patients with metastatic breast cancer who received a dose of capecitabine in combination with docetaxel, 68% had grade 3 or 4 neutropenia, 2.8% had grade 3 or 4 thrombocytopenia, and 9.6% had grade 3 or 4 anemia.

- **Geriatric Patients:** Patients ≥80 years old may experience a greater incidence of grade 3 or 4 adverse reactions. In 875 patients with either metastatic breast or colorectal cancer who received capecitabine monotherapy, 62% of the 21 patients ≥80 years of age treated with capecitabine experienced a treatment-related grade 3 or 4 adverse event: diarrhea in 6 (28.6%), nausea in 3 (14.3%), hand-and-foot syndrome in 3 (14.3%), and vomiting in 2 (9.5%) patients. Among the 10 patients 70 years of age and greater (no patients were >80 years of age) treated with capecitabine in combination with docetaxel, 30% (3 out of 10) of patients experienced grade 3 or 4 diarrhea and stomatitis, and 40% (4 out of 10) experienced grade 3 hand-and-foot syndrome.

Among the 67 patients ≥60 years of age receiving capecitabine in combination with docetaxel, the incidence of grade 3 or 4 treatment-related adverse reactions, treatment-related serious adverse reactions, withdrawals due to adverse reactions, treatment discontinuations due to adverse reactions and treatment discontinuations within the first two treatment cycles was higher than in the <60 years of age patient group.

In 995 patients receiving capecitabine as adjuvant therapy for Dukes' C colon cancer after resection of the primary tumor, 41% of the 398 patients ≥65 years of age treated with capecitabine experienced a treatment-related grade 3 or 4 adverse event: hand-and-foot syndrome in 75 (18.8%), diarrhea in 52 (13.1%), stomatitis in 12 (3.0%), neutropenia/ granulocytopenia in 11 (2.8%), vomiting in 6 (1.5%), and nausea in 5 (1.3%) patients. In patients ≥65 years of age (all randomized population; capecitabine 188 patients, 5-FU/LV 208 patients) treated for Dukes' C colon cancer after resection of the primary tumor, the hazard ratios for disease-free survival and overall survival for capecitabine compared to 5-FU/LV were 1.01 (95% C.I. 0.80 – 1.27) and 1.04 (95% C.I. 0.79 – 1.37), respectively.

- **Hepatic Insufficiency:** Patients with mild to moderate hepatic dysfunction due to liver metastases should be carefully monitored when capecitabine is administered. The effect of severe hepatic dysfunction on the disposition of capecitabine is not known.

Refer to current package insert for full prescription drug information for capecitabine.

